10.2 Secondary study parameters/endpoints

Groin recurrence after IFL

When enough patients agree on the standard arm (Group A) we might be able to calculate the number of women who develop a groin recurrence within 24 months after a negative IFL procedure in 1st recurrent vulvar cancer.

This failure is calculated by:

Total number of women with groin recurrence in a groin after negative IFL procedure divided by the number of women with uni- or bilateral IFL procedure * 100%.

Feasibility of the SLN procedure in recurrent vulvar cancer.

This is the success rate of detection and retrieval of the sentinel node, both related to the number of women, as well as number of groins in whom the proposed SLN surgery is successfully performed. (Group B1-B2)

Prior to surgery the surgeon has to state what groin surgery should be done; ipsi or bilateral groin treatment and what treatment should be done in case the SLN is not visible, or not found during surgery (see section 5.1.2.).

Feasibility is calculated:

- in relation to participants / patients:

Total number of women with successful SLN procedure(s) as per preoperative defined protocol, divided by the number of women that undergo the SLN procedure * 100%

- per groins:

Total number of groins with successful SLN procedure (as per preoperative defined protocol), divided by the number of groins that should be treated with the SLN procedure * 100%

Unexpected SLN's

This consists of SLN's in groins previously treated with IFL and or radiotherapy and SLN's found at unpredicted place, beyond the border of the regular IFL treatment. (Group B1-B2)

- *SLN in groins previously treated with IFL and or radiotherapy*
 - calculation of unexpected SLN's after previous IFL and or radiotherapy of the groin;

Total number of successful SLN's procedures in groins after previous IFL or radiotherapy of the groin, divided by total number of groins in whom a SLN was retrieved *100%.

- *SLN found at unpredicted places*

Total number of SLN's found at unpredicted places (outside the region of IFL), divided by total number of groins treated *100%.

- *Involvement of unexpected SLN's*

Total number of tumour positive unexpected SLN's, divided by total number of unexpected SLN's *100%.

Tumour positive SLN's

- as absolute number, and in relation to participants / patients:

Total number of women with uni or bilateral tumour positive SLNs, divided by the number of women with a successful SLN procedure * 100%.

- per groins:

Total number of groins with tumour positive SLNs, divided by the number of groins with successful SLN procedure * 100%.

Tumour positive groins

- in relation to participants / patients with groin surgery (pathology only):

Total number of women with uni or bilateral tumour positive lymph nodes, retrieved either by SLN or by IFL, divided by the number of women that underwent groin surgery * 100% (including women included in the non-SLN cohort, excluding women that did not have groin surgery in groups B2 C).

- in relation to participants / patients with first vulvar cancer recurrence:

Total number of women with uni or bilateral tumour positive lymph nodes, retrieved either by SLN or by IFL, and all women experiencing a groin recurrence during 24 month follow up, divided by the number of women included in the current study * 100% (including women included in the non-SLN cohort, and women that did not have groin surgery in group B2 and C).

- per groin:

Total number of tumour positive nodes divided by the number of groins treated *100%.

Outcome quality of life

QoL measurements will be done at baseline and 6, and 12 months after surgery.

Linear description and comparison between standard treated and study arm treated patients will be performed. (Groups non SLN cohort, and A - C)

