3. STUDY DESIGN

Preferably a randomized clinical trial or a non-inferiority study should be performed to answer the questions of this study. Given the low incidence of vulvar cancer and the even lower incidence of recurrent vulvar cancer it is not feasible to perform a study other than a multicentre cohort study.

In the participating centres all patients older than 18 years, fit for surgical treatment, with a first vulvar cancer recurrence will be registered.

Standard imaging (i.e., chest, abdominal and groin CT scanning) is performed.

In the absence of distant or proven groin metastases, and when all other eligibility criteria (see Figure 1) are met, the study is proposed and discussed with the patient.

Patients will be informed by oral and written information about the standard treatment (i.e. IFL) and the SLN procedure as part of the study. Patients will be informed that it is possible that the SLN is not traced after injection or at surgery. They will be informed that, should this be the case, standard treatment should be uni- or bilateral IFL. However, from our retrospective study it has become obvious that not all patients will consent for groin treatment and particularly IFL. So three patient groups are identified in *the SLN cohort*. (Figure 1)

- A) Control group: patients who understand the study and choose the standard IFL treatment of the groin(s): These patients will be asked to participate in the conventional treatment arm, with similar questionnaires and follow up.
- B) Patients understanding the study and are willing to undergo a SLN procedure rather than IFL.
 - B1) Patients who agree on IFL(s) in case the SLN is not visible on the lymph scintigram, or not detected at surgery
 - B2) Patients who not agree on IFL(s) in case the SLN is not visible on the lymph scintigram, or not detected at surgery
- C) Patients who agree on vulvar surgery, but refuse any groin surgery. These patients will be asked consent to collect information regarding treatment and outcome, and to fill in the questionnaires.

After surgery *regular follow up* is planned, with visits at 3, 6, 9, 12, 15, 18, 21 and 24 months. For study purposes ultrasonography of the groins is performed at 6 and 12 months. At baseline, at 6 and 12 months QoL questionnaire and a lymph oedema query are requested (see 4.1.3. for questionnaires).

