4.4 Sample size calculation

Approximately 18% of women will have groin metastases at the moment of their first vulvar cancer recurrence. Of these, approximately 20% will be detected prior to surgery (based on imaging and FNA) and these women will not be offered a SLN procedure, but advised to undergo an IFL(s). They will be asked for the observational arm of the non SLN cohort. (See figure 2)

The remaining patients will be informed about the study, they can decide on standard IFL (group A) or refuse any surgery of the groin(s) (group C) In 75% of cases that undergo SLN (group B) it will be possible to retrieve the SLN. In approximately 14,5% of women undergoing a SLN procedure a tumour positive node will be present. It is not expected that the change of a successful SLN procedure relates to the presence or absence of a positive groin node. We expect to find a positive SLN in 11% of cases undergoing a SLN procedure, a negative SLN in 64%, and an unsuccessful procedure in 25%. This corresponds to respectively 10.5%, 61.8% and 24.1% of all included patients.

Percentage failure of SLN or IFL is known for neither procedure in the recurrent setting. In the primary setting groin recurrence after negative IFL and after negative SLN are both about 3%.

Sample size for V2SLN is calculated based on a conservatively estimated groin recurrence rate of 3%, with a maximum additional groin failure rate of SLN in local recurrent vulvar SCC of 5%. The sample size, considering an alpha of 0.10 and a beta of 0.20, is then calculated to be 150 patients with a first vulvar cancer recurrence undergoing a SLN procedure (group B) and a negative SLN (Figure 2) So, we expect that approximately 243 women with a 1st recurrence of vulvar cancer should be included in the study. Stopping rules with dynamic boundaries were constructed to guarantee the safety of the study by continuously monitoring the number of groin recurrences. See Appendix 1 for a detailed description of these stopping rules.

[figure not shown]

Figure 2 Flow diagram of calculation of sample size

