10.1 Primary study parameter(s)

Groin recurrence after SLN

The main study endpoint is the number of women who develop a groin recurrence within 24 months after a technically successful SLN procedure in which the SLN was free from tumour in recurrent vulvar cancer. The prognosis (survival) is related to failure, whether uni- or bilateral, therefore the primary endpoint relates to patients rather than groins.

Women should have a full groin node dissection in case of technical problems (SLN does not appear on the scintigraphy, or cannot be retrieved at surgery). So to calculate SLN failure the women with a groin failure after IFL will not be considered as failure of the SLN procedure.

Women that refuse to consent for standard treatment, i.e., an IFL when the SLN is not feasible (Group B2) will only be included in the analyses of the primary outcome if the SLN is retrieved.

This failure is calculated by:

Total number of women with groin recurrence in a groin after tumour-negative SLN procedure divided by the number of women with successful uni- or bilateral SLN procedure * 100%.

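### The formula for groin recurrence after IFL divides by all women with an IFL instead of those with a negative IFL, so the rate comes out too low

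*Protocol*

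**What the plan says.** Section 10.2 (Groin recurrence after IFL) makes the rate conditional: "When enough patients agree on the standard arm (Group A) we might be able to calculate the number of women who develop a groin recurrence". It covers 24 months from a negative IFL at first recurrence. The population in the text is thus Group A with a negative IFL.

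The formula that follows has the numerator "Total number of women with groin recurrence in a groin after negative IFL procedure", which is "divided by the number of women with uni- or bilateral IFL procedure". The denominator is limited neither to Group A nor to women whose IFL was negative.

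Group A is not the only source of IFLs:
- Section 4.4: women with metastases proven before surgery are advised to have an IFL and are asked for the non-SLN cohort.
- Section 5.1.6: a full IFL is advised after a positive SLN, although local protocol may advise radiotherapy.
- Section 10.1, on failed SLN procedures: "Women should have a full groin node dissection in case of technical problems". Group B1 agrees to this in advance (section 3); group B2 does not.

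**The concern.** A failure rate after a negative procedure needs women with a negative procedure in both numerator and denominator. Here the numerator is restricted and the denominator is not, so every woman with a positive IFL lowers the rate without being able to raise it.

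The rate matters because the protocol has no benchmark of its own. Section 4.4 says the failure percentage of IFL in the recurrent setting is unknown and takes about 3% from the primary setting. The primary objective is the safety of replacing IFL, and the accepted margin is an additional 5%. An IFL rate that is too low would make the SLN rate look worse beside it and would give a wrong impression of the 3% baseline. Section 10.3 also lists IFL failure among the outcomes for its univariate and multivariate analyses, so an unclear population carries forward.

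**Working it through.** **Inputs, all from section 4.4 unless noted.** "Approximately 18% of women will have groin metastases at the moment of their first vulvar cancer recurrence"; 20% of these are found before surgery; about 14.5% of women undergoing SLN have a positive node; SLN outcomes are 11% positive, 64% negative and 25% unsuccessful, stated as 10.5%, 61.8% and 24.1% of all included women; 150 negative SLNs are required; total 243; recurrence after a negative IFL about 3% (primary setting). The B2 share and the uptake of advised IFL are not given and are assumed below.

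**Reproducing the 243.**
- Found before surgery: 0.18 × 0.20 = 3.6%, leaving 96.4%.
- 150 / 0.618 = 242.7, i.e. 243.
- 10.5% + 61.8% + 24.1% = 96.4%. The three SLN outcomes use up everyone except the 3.6%, so the figure contains no allowance for Groups A and C. If A and C together took 10% or 30% of eligible women (assumed), the total needed would be 150 / (0.964 × 0.64 × 0.90) = 270 or 150 / (0.964 × 0.64 × 0.70) = 347.

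**Reading 1: the formula inherits Group A.** Assume the choice of IFL is unrelated to nodal status, so 14.5% of Group A are node-positive at IFL.
- Printed rate = true rate × share with a negative IFL = 3% × (1 − 0.145) = 2.6%.
- With the unrounded share, 14.4 / 96.4 = 14.9%, the result is again 2.6%.

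**Reading 2: the formula is taken literally over all IFLs at 243 women**, with every advised IFL done and no B2 women.
- Proven before surgery: 0.036 × 243 = 8.7
- SLN-positive: 0.105 × 243 = 25.5
- Failed SLN: 0.241 × 243 = 58.6
- Denominator: 8.7 + 25.5 + 58.6 = 92.8, about 93
- Known node-positive before the IFL: 8.7 + 25.5 = 34.2, i.e. 37%
- Node-negative at IFL, from the failed-SLN women: 58.6 × (1 − 0.149) = 49.8, about 50
- Printed rate for a true 3%: 0.03 × 49.8 / 92.8 = 1.5 / 92.8 = 1.6%

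If the B2 share rises and B2 women have no IFL:

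| B2 share (assumed) | Denominator | Known node-positive | Node-negative at IFL | True 3% shows as |
|---|---|---|---|---|
| 0% | 93 | 37% | 50 | 1.6% |
| 25% | 78 | 44% | 37 | 1.4% |
| 50% | 64 | 54% | 25 | 1.2% |

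This treats the 34 known-positive women as unable to enter the numerator. A completion IFL after a positive SLN can itself be tumour-free; such women could contribute recurrences, so the dilution is approximate.

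**Precision of a failed-SLN line.** With at most about 50 node-negative women, 2 recurrences give 4% with an exact 95% interval of 0.5% to 13.7%. With 25 women and 1 recurrence the interval is 0.1% to 20.4%. Both contain 3% and 8%.

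**The case against.** The strongest reply is that the formula opens by referring back to the failure just described, so Group A carries over. The feasibility formulas in 10.2 likewise leave their group to the text above, and where the protocol wants the non-SLN cohort counted it says so. This stands: Reading 1 is natural, and on it women with proven metastases and those with completion IFL never enter. It does not rescue the denominator, which still counts Group A women with a positive IFL.

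The primary formula in 10.1 is built the same way, so on Reading 1 the two rates would be diluted alike. That may keep them roughly comparable, but neither would then be the rate after a negative procedure that the text defines.

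Three stronger readings are tempting and are not supported:
- A reader might infer that known metastases inflate the IFL rate. The numerator is limited to negative IFL, so the main effect is dilution, in the opposite direction.
- A reader might infer that the plan expects Group A to be empty. No share is stated; the zero is only implied by the 96.4%. Section 3 treats A as a control group with follow-up, and 10.2 says openly that the rate depends on numbers.
- A reader might infer that about 58 failed-SLN women form a ready benchmark. That is an upper bound: B2 women decline IFL, section 5.1.2 notes that standard care omits groin surgery after a previous IFL, and Appendix 2 (A) foresees no further treatment after a failed contralateral SLN in lateral tumours. Section 4.4 says "It is not expected that the change of a successful SLN procedure relates to the presence or absence of a positive groin node"; it does not say that recurrence after IFL is the same in failed-SLN women as in women who choose IFL. Restricting the rate to Group A is a defensible choice.

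Finally, the rate is secondary, conditional and descriptive. The test and stopping rule in Appendix 1 use fixed rates of 3% and 8% and do not depend on it.

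**Conclusion.** The denominator is wrong as written. On either reading, women with a positive IFL are counted below the line and cannot appear above it, so the rate is too low. For a true 3% it shows about 2.6% within Group A, and about 1.6% or less over all IFLs.

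The first figure assumes that nodal status does not influence the choice of IFL. The second assumes 243 women, every advised IFL done and no B2 women. Both take the 3% from the primary setting.

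The consequence is limited to a descriptive rate and the exploratory analyses that use it; the primary conclusion is untouched. Separately, with no allowance for Groups A and C in the 243, there may be too few Group A women to report the rate at all.

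**What to change.** In 10.2:
- State Group A in the formula itself and make the denominator the number of women whose IFL nodes are all tumour-free.
- Say that completion IFL after a positive SLN and IFL for metastases proven before surgery are excluded.
- Report women with a node-negative IFL after a failed SLN procedure as a separate descriptive line with an exact 95% interval, and say that it cannot separate 3% from 8%.
- Check the denominator in 10.1 at the same time, so that the two rates have the same base.

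In 4.4, state the expected share of Groups A and C, or say that the 243 allows for none and that the Group A rate may not be obtainable.

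The cost is analysis wording. The surgery, pathology and 24-month follow-up forms in Appendix 4 already cover the data, and treatment is unchanged. The one loss is a somewhat less precise rate from a smaller denominator.

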8.1.2 Secondary study parameters/endpoints

Feasibility of the SLN procedure in recurrent vulvar cancer

This is the success rate of detection and retrieval of the sentinel node, both related to the percentage of women, as well as groins in whom the proposed SLN surgery is successfully performed.

Perioperative and postoperative morbidity and mortality

Data collection at 6 weeks after every surgery by the physician. Type of surgery (SLN right groin, SLN left groin, IFL right, IFL left, vulva surgery, reconstructive surgery). Location of SLN found (within IFL region or not), surgical challenges (unintended lesion of vena saphena magna, bleeding, others), duration of surgical procedure, complications (wound infections, wound breakdown, lymph oedema (see adverse effect Appendix 1)), length of hospital stay, re-surgery, readmission.

Incidence of tumour positive sentinel nodes

All specimen will be examined according to the protocol (See section 5.1.) depth of tumour infiltration, presence of LVSI, number of SLN's per groin, number of removed nodes per groin.

Adjuvant treatment

Adjuvant groin treatment; IFL, and or radiotherapy.

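### In 10.2, the percentage for sentinel nodes at unpredicted places divides nodes by groins, so it is a proportion of neither (minor)

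*Protocol*

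**What the plan says.** Protocol 10.2, under _Unexpected SLN's_ (groups B1 and B2), defines the term: "This consists of SLN's in groins previously treated with IFL and or radiotherapy and SLN's found at unpredicted place, beyond the border of the regular" (the sentence ends by naming the inguinofemoral dissection). Three percentages follow.

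1. Previously treated groins: the count of successful procedures in groins with earlier IFL or irradiation, which is then "divided by total number of groins in whom a SLN was retrieved *100" percent.
2. Unpredicted places: "Total number of SLN's found at unpredicted places (outside the region of IFL), divided by total number of groins treated *100" percent.
3. Involvement: "Total number of tumour positive unexpected SLN's, divided by total number of unexpected SLN's *100" percent.

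Section 8.1.2 lists among the data to be collected "number of SLN's per groin, number of removed nodes per groin", and also whether each sentinel node lay within the IFL region. Section 5.1.3 has the surgeon continue looking for further sentinel nodes when residual radioactivity in the biopsy bed is high enough.

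Elsewhere 10.2 uses a consistent per-groin form, for tumour-positive sentinel nodes: "Total number of groins with tumour positive SLNs, divided by the number of groins with successful SLN procedure * 100" percent. The per-groin line under _Tumour positive groins_ does not: it places a count of positive nodes over the groins treated. Section 10.3, _Additional analyses_, names unexpected nodes among the outcomes for univariate analysis followed by multivariate logistic regression.

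**The concern.** The second formula is written as a percentage, but its numerator is not a subset of its denominator. A groin with two aberrant sentinel nodes counts twice above the line and once below it. The protocol also does not say which groins count as treated. They could be all groins explored, only those with a sentinel node retrieved, or also those given IFL after a failed procedure.

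Drainage outside the normal IFL field is part of the argument for the study. The Introduction reports it in the retrospective series, and 11.4 says that women with such a pattern might benefit. The Introduction counts it by groin and 11.4 by patient. A nodes-over-groins ratio can be compared with neither. Nor does it supply the yes/no outcome per unit that the logistic regression in 10.3 needs.

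**Working it through.** The protocol states no expected value for this percentage, so there is no figure to reproduce. The check is of units, followed by simple ratios.

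**Units of each formula**

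| Formula in 10.2 | Numerator | Denominator | Proportion? |
|---|---|---|---|
| 1. Previously treated groins | groins (successful procedures) | groins with a retrieved SLN | yes |
| 2. Unpredicted places | nodes | groins treated (undefined) | no |
| 3. Involvement | nodes | nodes | yes |
| Tumour positive groins, per groin | nodes | groins treated (undefined) | no |

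**Effect on formula 2**

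Let G be the groins in the denominator, A the groins with at least one SLN outside the IFL region, and m the mean number of such nodes per affected groin.

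- As written: A × m / G.
- Proportion of groins affected: A / G.
- The formula is therefore m times the proportion of affected groins, and it passes 100% when m exceeds G / A.

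Inputs from the Introduction: G = 44 groins in the retrospective series and A = 2 groins with nodes beyond the normal IFL borders. The value of m is not given; 1 to 3 is an assumed range.

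| m (assumed) | As written | Groins affected |
|---|---|---|
| 1 | 2/44 = 4.5% | 2/44 = 4.5% |
| 2 | 4/44 = 9.1% | 2/44 = 4.5% |
| 3 | 6/44 = 13.6% | 2/44 = 4.5% |

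The number of affected groins is the same in every row.

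**No upper bound.** As an invented illustration, 10 groins treated with 6 of them holding 2 such nodes gives 12/10 = 120%.

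**Undefined denominator.** The Introduction says that the procedure could be performed as planned in 84% of the 44 groins: 0.84 × 44 = 36.96, about 37. If those are taken as the groins with a retrieved node, which the protocol does not say, the groin-level figure is 2/37 = 5.4%, against 2/44 = 4.5% on all groins.

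The same algebra applies to the per-groin line under _Tumour positive groins_, with A as groins holding at least one positive node and m as positive nodes per such groin.

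**The case against.** The strongest reply is that this is a descriptive secondary figure with no hypothesis or target. It is not named in the objectives, and it could be corrected at reporting from the raw counts. That is fair and sets the severity. It does not make the formula right: followed as written, it gives a percentage with no defined meaning.

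A second reply is that the direction of distortion is not fixed. With one node per affected groin the formula gives 4.5%, which is below the 5.4% on about 37 groins. Counting several nodes raises the figure, and including groins without a retrieved node lowers it. This stands, so it cannot be said that the formula must overstate aberrant drainage. A denominator of all groins explored would also be legitimate if it were stated.

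A reader might infer that all three formulas for unexpected nodes are faulty. The documents do not support that.

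- Formula 1 counts groins on both sides, and its numerator is contained in its denominator. It is a valid share: previously treated groins among those with a retrieved node. It is not a detection rate in previously treated groins, but the protocol does not call it one. That question is covered by the per-groin feasibility endpoint in 10.2, whose denominator is the groins meant to have the procedure, and 10.3 analyses feasibility by previous groin treatment.
- Formula 3 is nodes over nodes. Both parts of the definition of an unexpected SLN refer to nodes, so it is a proper proportion. A line saying that a node meeting both descriptions counts once would help, but its absence is not an error.
- Section 11.4 supports the importance of nodes outside the IFL margins. It does not discuss nodes found after previous IFL, so it adds nothing against formula 1.

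**Conclusion.** The point holds for two lines of 10.2: the formula for nodes at unpredicted places and the per-groin line under _Tumour positive groins_. Both put nodes over groins, leave the treated groins undefined, and can exceed 100%.

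For the first, the reported figure is inflated by a factor equal to the mean number of aberrant nodes per affected groin, relative to the share of affected groins on the same denominator. On the retrospective counts the spread is 4.5% to 13.6% over an assumed 1 to 3 nodes per groin. If every affected groin held exactly one such node there would be no inflation, but the protocol plans for several.

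Severity is minor. The primary endpoint, sample size and stopping rule do not use either line.

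**What to change.** In 10.2, replace the formula for unpredicted places with: groins with at least one SLN outside the IFL region, divided by groins in which an SLN was retrieved, times 100%. List the number of such nodes beside it. This figure is bounded by 100%, counts groins as the Introduction does, and gives a yes/no outcome per groin for the regression in 10.3.

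Replace the per-groin line under _Tumour positive groins_ with: groins with at least one positive node, divided by groins treated, times 100%, and state which groins count as treated.

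Formulas 1 and 3 can stay.

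The cost is two reworded lines. Section 8.1.2 already provides for recording SLN location relative to the IFL region and the number of SLNs per groin. The content of the case report forms is not shown, so it is worth confirming that location can be linked to the groin.

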4.3 Exclusion criteria

A potential subject who meets any of the following criteria should not undergo the SLN procedure in the study arm (A-B), the patient can be asked for the non SLN cohort.

- Inoperable tumours and tumours with diameter > 4 cm.
- Patients with inguinofemoral lymph nodes at palpation clinically suspect for metastases, at radiology enlarged (> 10 mm short axis) / suspicious groin nodes and with cytological proven inguinofemoral lymph node metastases.
- A history of bilateral IFL **and** radiotherapy to the groins.
- A lateral tumour and history of ipsilateral IFL **and** ipsilateral radiotherapy.
- Tumour encroaching urethra, vagina, or anus.
- Previous surgery of the vulva was not radical (margin < 1 mm) and additional treatment (2nd surgery or radiotherapy) was not performed.
- Multifocal recurrent disease of the vulva.
- Synchronous, non- curable 2nd malignancy.

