13.2 Synthesis

Since the majority of patients with recurrent vulvar cancer are frail, an observational study of accuracy, in which a SLN biopsy and an IFL are done during the same surgical procedure and in which the accuracy of the SLN is confirmed in the IFL is not feasible: too many frail women will refuse this extensive surgery.

In general, little information is available on groin recurrences and outcome of treatment in recurrent vulvar cancer. To reduce the knowledge gap we will ask all patients for either the non- SLN cohort (observational study) (in case an IFL is done because of a proven groin metastases) or the V2SLN study as described with the possibility for the patient to choose for a SLN procedure (or not).

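### The all-women groin-positivity rate in 10.2 has no numerator route for metastasis proven by FNA or biopsy at baseline in women without groin surgery, so it can be too low

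*Protocol*

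**What the plan says.** Under Tumour positive groins, section 10.2 gives two rates per woman. The first uses pathology alone and is restricted, above and below the line, to women who had groin surgery. The second relates to all women with a first recurrence. Its numerator is women with positive nodes "retrieved either by SLN or by IFL, and all women experiencing a groin recurrence during 24 month follow up". Its denominator is every woman in the study, and the text names the non-SLN cohort and the unoperated women of groups B2 and C as included.

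Section 4.4 starts from the premise "Approximately 18% of women will have groin metastases at the moment of their first vulvar cancer recurrence" and continues "Of these, approximately 20% will be detected prior to surgery (based on imaging and FNA" in brackets. IFL is advised for these women, and "They will be asked for the observational arm of the non SLN cohort". Section 4.3 lists cytologically proven groin metastases, and also inoperable tumours, among the reasons for not doing an SLN procedure, and adds that "the patient can be asked for the non SLN cohort". Section 3 gives that cohort individualised standard care and does not make groin surgery a condition of entry. Section 13.2 describes entry to the non-SLN cohort as "in case an IFL is done because of a proven groin metastases".

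**The concern.** The second rate is deliberately wider than surgical pathology: it adds later groin recurrences so that unoperated women can still be found positive. Yet it leaves out the most direct non-surgical evidence, a metastasis already proven before treatment. Women with such proof go to the non-SLN cohort and so are in the denominator. If they have no SLN or IFL specimen, the formula as written scores them as free of groin disease unless a recurrence is recorded.

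The recurrence route is not a dependable rescue. A proven node that is not resected is persistent disease rather than clearly a recurrence. Also, section 8.3 describes the 6- and 12-month groin ultrasound only for women treated with the SLN procedure.

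The protocol leaves room for such women. Section 4.3 allows inoperable women into the cohort. Section 5.1.2 notes that the current standard omits groin surgery after a previous IFL. Section 1 reports that groin surgery was often not done despite the guideline, and section 3 expects some women to refuse it. At stake is whether a descriptive rate for all first recurrences depends on how a known positive was treated.

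**Working it through.** **Inputs, all from section 4.4.** Groin metastases at first recurrence: 18%. Share of these detected before surgery: 20%. SLN retrieval: 75%. Positive node among women undergoing SLN: 14.5%. Women needed with a negative SLN: 150.

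**Reproducing the plan's figures.**
- Detected before surgery: 0.18 × 0.20 = 0.036. Remaining: 1 − 0.036 = 0.964.
- Positive SLN: 0.75 × 0.145 × 0.964 = 10.5% of all women.
- Negative SLN: 0.75 × 0.855 × 0.964 = 61.8%.
- Unsuccessful procedure: 0.25 × 0.964 = 24.1%.
- Total to include: 150 / 0.618165 = 242.7, rounded up to 243.

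These match the 10.5%, 61.8%, 24.1% and 243 in the protocol. The three percentages add to 96.4%, so the remaining 3.6% are the women detected before surgery: 0.036 × 243 = 8.7, about 9.

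**Rate under the formula as written.** Let *u* be the share of baseline-proven women who have neither a groin specimen nor a counted recurrence. If every other metastasis is found by surgery or recurrence,

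reported rate = 18% − 3.6% × *u*.

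The protocol gives no value for *u*, so the whole range is shown.

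| *u* (assumed) | Reported rate | Shortfall, points | Women missed of 243 |
|---|---|---|---|
| 0% | 18.0% | 0 | 0 |
| 10% | 17.6% | 0.4 | 0.9 |
| 20% | 17.3% | 0.7 | 1.7 |
| 50% | 16.2% | 1.8 | 4.4 |
| 100% | 14.4% | 3.6 | 8.7 |

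The outer bound is 3.6 / 18 = 20% in relative terms. With baseline proof added to the numerator, the expected rate is 18.0% (0.18 × 243 = 43.7 women) whatever *u* is.

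**Scale.** The 95% half-width for 18% with 243 women is 1.96 × √(0.18 × 0.82 / 243) = 4.8 points. Even the outer bound is smaller than that. But the shortfall is systematic, and a confidence interval would not reveal it.

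**The case against.** A reader might infer that prevalence at first recurrence is certainly understated, by a sizeable fraction. The documents do not support that, for three reasons.

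First, the planned path for these women is surgical. Section 4.4 says IFL is advised, and section 13.2 speaks of entry "in case an IFL is done because of a proven groin metastases". A woman who follows that path enters the numerator through her IFL specimen, and if all do, this source adds no bias. The 100% row supposes that none does. This stands, and it is why the low end of the table is the more plausible.

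Second, the net direction is not settled. The numerator also counts every groin recurrence over 24 months, some of which may be new spread rather than disease present at first recurrence. That pushes the rate up. This stands too: the omission by itself can only lower the rate, but the reported rate could err either way.

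Third, a reader might treat this rate as the study's replacement for the 18% in section 4.4. No section says so. Section 2 does not list nodal prevalence as an objective, and the knowledge gap in section 13.2 concerns groin recurrences and treatment outcome.

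Two lesser points also hold. The surgery-only rate just before it is free of this mismatch, though it answers a narrower question. And the flow in section 4.4 does not cover women excluded for tumour size, multifocality or encroachment, for whom no positivity rate is given; with them in the denominator the effect could be smaller or larger.

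None of this changes the reading of the formula: a known positive without groin surgery is scored negative unless a recurrence is recorded.

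**Conclusion.** The point holds as a gap in the definition of one descriptive secondary rate. Women with groin metastasis proven at baseline are always in the denominator, but reach the numerator only through an SLN or IFL specimen or a recorded recurrence. On the figures in section 4.4 the omission can lower the rate by 0 to 3.6 points, that is, by 0 to about 9 of 243 women. Because IFL is advised, a shortfall well below the upper bound is more likely. The size rests on the protocol's 18% and 20%, on an assumed share without a specimen or counted recurrence, and on all other metastases being found. The primary endpoint, the 150 and 243 women, and the stopping rule are not touched.

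**What to change.** In the numerator of the second rate in section 10.2, add: *or groin metastasis cytologically or histologically proven at baseline*. Count each woman once. Report three components separately: proven at baseline, found at surgery, and first shown by a later groin recurrence. The split lets a reader set aside recurrences that may be new spread.

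The cost is one phrase and a three-line breakdown, with no change to treatment, follow-up or sample size. Groin-node status is already established for eligibility. Appendix 4 lists an eligibility form, a form for the current tumour and lymph nodes, and a preoperative ultrasound form with a copy of the report. No form listed there names FNA or cytology, so check that the result is recorded as a field.
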